7.4. Sample Size and Power Calculation

The primary endpoint of the study is to establish that stepped PC is non-inferior to early integrated PC in the change in QOL, as measured by the FACT-L at week-24. Although the primary endpoints in our previous studies assessed the change in FACT-L from baseline to week-12, we chose to focus on QOL at 24 weeks as the life-expectancy of patients with advanced lung cancer has improved over the last few years. Thus, examining QOL at 12 weeks may overlook important differences between groups as the disease progresses. In our most recent trial of early integrated PC versus standard oncology care, we observed a 7.5-point difference in the FACT-L at week-24 favoring the integrated PC group. Thus, we chose a conservative non-inferiority margin of 4.5 points, which is slightly less than 50% of the previously observed advantage with early integrated PC compared to oncology care alone. As a 6-point difference in FACT-L score is considered the lowest range of a clinically meaningful difference, our non-inferiority margin would not reach the threshold of clinically meaningful difference in QOL.⁵⁵ With

188 patients per group, we will have >80% power to establish the non-inferiority of stepped PC compared to early integrated PC on the FACT-L with a one-sided alpha of 0.05, and a non-inferiority margin of 4.5 points. We are currently observing 35% missing data across sites at 24 weeks, primarily due to progressive illness or death. Therefore, we increased our sample size to 255 per group to ensure we have adequate power to assess for non-inferiority of stepped PC.

Our study also has adequate power to assess for non-inferiority of stepped PC compared to early integrated PC in EOL communication and hospice length-of-stay. With a sample size of 510, we will have >80% power, with a one-sided alpha of 0.05, to reject the hypothesis that patient-reported EOL communication with stepped PC would be 10% lower than early integrated PC, assuming that the rate of EOL communication in the early integrated PC group is 30% (based on our recent trial). With this sample size, we will also have >80% power to establish the non-inferiority of stepped PC compared to early integrated PC in hospice length-of-stay with a one-sided alpha of 0.05, and a non-inferiority margin of 7 days. We were conservative with our power estimations by using the highest observed standard deviation for all outcomes from prior studies.

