We recently found that improvements in QOL and depression with PC are mediated through use of adaptive coping skills, and prior studies have shown that age, gender, and race can moderate the impact of PC in patients with cancer.^{63,64} Therefore, we will conduct bootstrapped tests of mediation to determine whether group differences in the FACT-L are mediated by improved coping or other potential mediators such as psychological distress. Additionally, we will explore potential moderators of the interventions to ensure generalizability and identify whether certain groups benefit more from one of the two PC models. We will create interaction terms for the linear regression and linear mixed models to examine whether differences in FACT-L are moderated by patient factors (e.g., age, gender, race, baseline distress), disease or treatment factors, or study site.

The secondary aim of the study is to assess whether stepped PC is non-inferior to early integrated PC with respect to patient-clinician communication about EOL care preferences and length of stay in hospice. We will examine patient report of discussing EOL care preference with their clinicians using the following item: “Have you and your doctors discussed any particular wishes you have about the care you would want to receive if you were dying?” Although patients will complete this measure repeatedly during the course of the study, we will use the patient’s final assessment for this analysis. We will assess differences between study arms in the rate of patients reporting “yes” to this item using a one-sided alpha of 0.05 and a non-inferiority margin of 10%. The difference in rates between study arms will be assessed using a generalized linear regression model specified with an identity link function and binomial response probability distribution with adjustment for the randomization stratification factors and any demographic and clinical variables that are imbalanced between groups.

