### *Missing Data*

Primary analyses will include available data without imputation of missing data. The characteristics of patients who complete versus do not the week 24 survey will be compared descriptively. Sensitivity analyses will explore how different assumptions about the missing data mechanisms affect estimated outcomes. These sensitivity analyses may include multiple imputation, terminal decline joint modeling, or partially conditional models, which provide estimates of the mean conditional on being alive and observed at each timepoint.

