#### *Secondary Outcomes*

The difference between groups in the rate of patient-clinician communication about EOL care preference at the final follow-up assessment will be assessed using a generalized linear regression model specified with an identity link function and binomial response probability distribution. The model will include group assignment (stepped PC vs early integrated PC) and randomization stratification factors as main effects. Using the pre-specified non-inferiority margin of 10%, the nominal p-value for non-inferiority will be calculated using a one-sided test of the estimated difference in rates against a null value of -10%. Non-inferiority of stepped PC will be established if the nominal p-value is significant after application of the multiplicity adjustment procedure for secondary outcomes. Model-based estimates of the rate with 95% CI in each group, the difference in rates between groups and its 90% CI, the nominal p-value, and the multiplicity-adjusted p-value will be reported.

The difference between groups in the mean length of stay in hospice among patients who die during the study will be assessed using a linear regression model with main effects for group assignment (stepped PC vs early integrated PC) and randomization stratification factors. Using the pre-specified non-inferiority margin of 7 days, the nominal p-value for non-inferiority will be calculated using a one-sided test of the estimated difference in rates against a null value of -7. Non-inferiority of stepped PC will be established if the nominal p-value is significant after application of the multiplicity adjustment procedure for secondary outcomes. Model-based estimates of the mean with 95% CI in each group, the difference in means between groups and its 90% CI, the nominal p-value, and the multiplicity-adjusted p-value will be reported.

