#### *Exploratory Outcomes*

The rate of change in quality of life from baseline to week 48 (assessed by the FACT-L) will be compared between groups using a linear mixed effects regression model. This model will utilize FACT-L scores at each timepoint, with estimation via maximum likelihood. The model will include fixed effects for group assignment (stepped PC vs early integrated PC), time from baseline (in weeks), time-by-group interaction, and randomization stratification factors, as well as random intercepts for each patient.

Model-based estimates of the slope with 95% CI in each group and the difference in slopes between groups and its 95% CI will be reported.

The difference in means between intervention groups in patient-reported depression symptoms (assessed by PHQ-9) and coping strategies (assessed by subscales and higher-order factors of Brief Cope) at week 24, will be estimated for each outcome using a linear regression model with group assignment (stepped PC vs early integrated PC) and baseline score, as well as randomization stratification factors, as main effects. Model-based estimates of the mean with 95% CI in each group and the difference in means between groups and its 95% CI will be reported.

Rates of prognostic understanding at week 24, based on PTPQ items eliciting the patient's goal of cancer care ("to cure my cancer" vs any other option) and the patient's assessment of curability ("yes" vs "no") will be compared using generalized linear models specified with an identity link function and binomial response probability distribution. Model-based estimates of the rate with 95% CI in each group and the difference in rates between groups and its 95% CI will be reported.

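### The quoted power of more than 80% for end-of-life communication assumes that all 510 patients are analysed, and the baseline answer to the same item is not used

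*Protocol*

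**What the plan says.** Protocol 7.4 gives the EOL power claim as "With a sample size of 510, we will have >80% power, with a one-sided alpha of 0.05, to reject the hypothesis" of a 10-point deficit, "assuming that the rate of EOL communication in the early integrated PC group is 30" percent. Just before this, for the primary endpoint only, it enlarges the sample because "We are currently observing 35% missing data across sites at 24 weeks, primarily due to progressive illness or death". Protocol 7.5 repeats the one-sided 0.05 level and the 10-point margin.

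On who is analysed, Protocol 7.5 refers to the patient's "final assessment for this analysis", and SAP 6 also speaks of the final assessment. SAP 9 is more specific: "communication about EOL care preference at the final follow-up assessment will be assessed using a generalized linear regression model". SAP 8 adds: "Primary analyses will include available data without imputation of missing data".

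On the EOL model, SAP 9 says: "The model will include group assignment (stepped PC vs early integrated PC) and randomization stratification factors as main effects". The baseline answer is not included, although Protocol Table 1 and SAP Table 1 schedule the questionnaire (PTPQ) at baseline and at weeks 12, 24, 36 and 48. By contrast, depression and coping are analysed with a "linear regression model with group assignment (stepped PC vs early integrated PC) and baseline score, as well as randomization stratification factors, as main effects", and the FACT-L model also adjusts for its baseline score.

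**The concern.** A patient with no follow-up PTPQ contributes nothing to the planned EOL analysis, so 510 is the number before loss and not the number analysed. The protocol allows for loss in the primary endpoint but not here.

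EOL communication is one of the key secondary hypotheses in SAP 2, and Protocol 7.4 calls its power adequate. An inconclusive result would be read against a figure that is borderline even with complete follow-up.

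Two related points follow. If the shorter wording in Protocol 7.5 and SAP 6 were taken to let a baseline answer count as final, N would stay at 510. But those answers predate randomisation and would pull the arms together, which favours non-inferiority. Separately, the plan collects a covariate that could recover some precision and does not use it.

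**Working it through.** **Inputs.** 255 per arm, control rate 0.30 and one-sided 0.05 (z = 1.645) from Protocol 7.4; margin 0.10 from Protocol 7.4 and 7.5 and SAP 9. Two inputs are not stated: the true stepped-care rate and the share with no follow-up PTPQ. For the first I take both plausible readings. For the second I vary the loss from 0% to 36%, the top being the week-24 rate in SAP 7.

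**Step 1: reproduce the plan's figure at full N.**
- Equal rates (30% in both arms): SE = sqrt(2 × 0.3 × 0.7/255) = 0.0406; power = Φ(0.10/0.0406 − 1.645) = 79.4%. Score-variance (Farrington-Manning) and exact calculations also give 79.4%. Reaching 80% needs 260 per arm.
- 30% vs 20%, pooled null variance: SE0 = sqrt(2 × 0.25 × 0.75/255) = 0.0383; SE1 = sqrt((0.21 + 0.16)/255) = 0.0381; power = Φ((0.10 − 1.645 × SE0)/SE1) = 83.4%. For 80%, n = 231, so tolerated loss is 1 − 231/255 = 9.4%.
- 30% vs 20%, unpooled: power = Φ(0.10/0.0381 − 1.645) = 83.7%. For 80%, n = 229, so tolerated loss is 10.2%.

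The stated figure therefore reproduces at full N under the 30%-vs-20% reading, and falls just short under the equal-rates reading.

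**Step 2: apply loss, n = 255 × (1 − loss).** Power in %, as equal rates / pooled 30 vs 20 / unpooled 30 vs 20:

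| Assumed loss | n per arm | One-sided 0.05 | One-sided 0.10 |
|---|---|---|---|
| 0% | 255 | 79.4 / 83.4 / 83.7 | 88.1 / 90.9 / 91.0 |
| 10% | 229.5 | 75.6 / 79.8 / 80.1 | 85.5 / 88.5 / 88.7 |
| 20% | 204 | 71.2 / 75.6 / 75.9 | 82.2 / 85.5 / 85.7 |
| 36% (upper-end case) | 163.2 | 62.8 / 67.2 / 67.6 | 75.5 / 79 / 79 |

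**Step 3: the level that will probably apply.** Benjamini-Hochberg at 0.15 over three tests has thresholds 0.05, 0.10 and 0.15. If the visit-count test is rejected, any EOL p-value of 0.10 or less is also rejected. Protocol 5.3.1 expects medians of 7 visits and, on step 1, 3 visits by week 24. Treating these as means, with an assumed SD of 10 visits, SE = 10 × sqrt(2/255) = 0.886. At two-sided 0.05, power is Φ(4/0.886 − 1.96) = 99.5%, or 92.3% if step-up narrows the difference to 3 visits. At 0.10, 80% EOL power needs 190, 169 or 167 per arm, which tolerates 25.5%, 33.7% or 34.5% loss.

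**Step 4: if baseline-only answers counted as final.** With a share f of such patients, a true deficit of 10 points among followed patients shrinks to 10 × (1 − f). The chance of wrongly claiming non-inferiority at 0.05 is Φ(0.10f/SE − 1.645), with SE taken from the diluted rates at 255 per arm. This gives 6.5%, 8.4% and about 13% for f = 5%, 10% and 20%, instead of 5%.

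**Step 5: what the baseline answer could add.** Approximating the gain by n/(1 − r²), at 10% loss and r = 0.3 the effective n is 229.5/0.91 = 252, and power is 79.0% against 75.6% unadjusted. Simulation (40,000 runs, 230 per arm, standardised logistic model, blank baseline items kept as a category) gave about 77%, 79% and 82% for correlations of 0.2, 0.3 and 0.4. Rejection at the margin stayed at 5.0% to 5.2%. A check with a linear model on the identity scale gave similar gains of about 2 to 6 points.

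**The case against.** The strongest reply is that nothing is miscalculated: Protocol 7.4 describes a contrast of 30% with a rate 10 points lower, and that calculation does exceed 80%. The equal-rates shortfall is only 0.6 points. Stratification factors explaining about 1.8% of the outcome variance would close it (255/0.982 = 259.7), though the documents give no such figure. This stands as far as full N is concerned.

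The relevant loss is also unknown. The 35% and 36% figures are for week 24, whereas any answer at week 12, 24, 36 or 48 suffices, so the share with none should be lower. That is right, and it has not been shown that loss exceeds 10%. But the plan does not show that it stays below 10% either, and no formula tried supports the claim beyond that.

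The decision rule is Benjamini-Hochberg, not a fixed 0.05. This also stands and is the main reason the point is minor. It does not support the figure as written, because Protocol 7.4 and 7.5 both tie it to 0.05.

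SAP 9 already says follow-up, so the baseline-only reading needs only a clarifying sentence. Omitting the baseline answer is consistent with the plan's other PTPQ models, and the gain cannot be predicted because no correlation is given. Finally, enrolment is complete, so restated power changes no decision; the 90% CI will show the precision achieved. All of this is fair, and it limits the remedy to documentation plus one covariate.

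**Conclusion.** The point holds, as a minor one. The power of more than 80% at one-sided 0.05 is quoted on all randomised patients, while the analysis uses only those with a follow-up answer. At full N it is borderline: 79.4% or about 83.5%, depending on a formula the plan does not name. It survives at most about 10% loss.

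Under the likely Benjamini-Hochberg threshold of 0.10 or looser, power is at least 80% up to about 25% loss (about 34% with the 30%-vs-20% formulas), so practical harm is mild. That relief assumes the visit-count test is rejected, which is very likely under the assumed SD.

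Leaving out the baseline answer is a missed efficiency gain of unknown size, not an error. The primary endpoint is not affected.

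**What to change.** Use one dated SAP addendum, a route the SAP already follows.

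1. Restate EOL power at the expected number of patients with at least one post-baseline PTPQ. Name the formula, the assumed stepped-care rate and the level (0.05, and under Benjamini-Hochberg). Use the planning rate of 30%, not observed rates. State that a baseline-only answer is not a final assessment. Do not enlarge the trial.
2. Before EOL data are analysed, add the baseline answer to the planned identity-link model, with a blank baseline answer as its own category so that no patient is lost. If the model does not converge, standardise from a logistic model. Report the adjusted risk difference with its 90% CI. If EOL data have already been analysed, report this as a sensitivity analysis beside the planned model. Confirm the item wording first, because Protocol 5.2 words it differently from Protocol 7.5 and SAP 6.
3. As a lesser matter, hospice power is also quoted on 510 although the SAP analyses patients who die. State the SD and the expected number of deaths, and use that number in the normality argument in Protocol 7.5.

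The cost is one addendum entry and one covariate already collected, with no extra patients or visits. The stated EOL power becomes less favourable.

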7.5. Analysis Plan

The primary endpoint of the study is to establish that stepped PC is non-inferior to early integrated PC in QOL, as measured by the FACT-L at week-24. We will begin with descriptive and graphical summaries of the endpoints to evaluate whether the normality assumption is reasonable or if transformation is necessary. Based upon our prior study demonstrating statistical and clinically meaningful between group differences in the FACT-L at 24-weeks, the primary endpoint to compare patient FACT-L scores at week-24 between the study groups using a linear regression model controlling for randomization stratification factors, baseline values, and demographic and clinical factors (as necessary for any imbalances in baseline variables). We will also use linear mixed models of the longitudinal data, allowing us to account for dependency among means over time and to control for demographic and clinical factors when examining change between groups in QOL across multiple time points. We will also compare the number of PC visits between the two groups to ensure that the stepped PC model led to a reduction in PC visits.

We will compare depression (PHQ-9) and coping strategies (Brief Cope, including higher-order factors of the Brief Cope in our sample⁵²: active coping & avoidant coping) at week-24 between groups using linear regression models controlling for randomization

stratification factors, baseline values and selected demographic and clinical factors. We will then evaluate linear mixed models of the longitudinal data, as described above, to examine changes in these outcomes between groups across multiple time points.

To compare illness understanding as measured by the PTPQ between the two groups at week-24, we will analyze appropriate items using the appropriate model for the outcome of interest (e.g., linear regression or generalized linear models with an identity link function and binary response probability distribution) with adjustment for randomization stratification factors and any demographic and clinical factors that are imbalanced to assess differences between groups.

We recently found that improvements in QOL and depression with PC are mediated through use of adaptive coping skills, and prior studies have shown that age, gender, and race can moderate the impact of PC in patients with cancer.^{63,64} Therefore, we will conduct bootstrapped tests of mediation to determine whether group differences in the FACT-L are mediated by improved coping or other potential mediators such as psychological distress. Additionally, we will explore potential moderators of the interventions to ensure generalizability and identify whether certain groups benefit more from one of the two PC models. We will create interaction terms for the linear regression and linear mixed models to examine whether differences in FACT-L are moderated by patient factors (e.g., age, gender, race, baseline distress), disease or treatment factors, or study site.

The secondary aim of the study is to assess whether stepped PC is non-inferior to early integrated PC with respect to patient-clinician communication about EOL care preferences and length of stay in hospice. We will examine patient report of discussing EOL care preference with their clinicians using the following item: “Have you and your doctors discussed any particular wishes you have about the care you would want to receive if you were dying?” Although patients will complete this measure repeatedly during the course of the study, we will use the patient’s final assessment for this analysis. We will assess differences between study arms in the rate of patients reporting “yes” to this item using a one-sided alpha of 0.05 and a non-inferiority margin of 10%. The difference in rates between study arms will be assessed using a generalized linear regression model specified with an identity link function and binomial response probability distribution with adjustment for the randomization stratification factors and any demographic and clinical variables that are imbalanced between groups.

We will assess the non-inferiority of hospice length-of-stay between stepped PC and early integrated PC using linear regression model controlling for randomization stratification factors, as well as demographic and clinical factors that are imbalanced at baseline, with a one-sided alpha of 0.05 and a non-inferiority margin of 7 days. Although hospice length-of-stay is not normally distributed, based on a sample size of 510, the means would have a normal distribution (central limit theorem). We will also perform the Wilcoxon rank sum test to compare our results to those obtained with linear regression. We will also test whether differences in EOL outcomes are mediated by prognostic

awareness or moderated by patient factors (e.g., age, gender, race), disease or treatment factors, or study site as described in aim 1.

We will also compare PC resource utilization and cost effectiveness of stepped PC versus early integrated PC. We will assess the superiority of stepped PC compared to early integrated PC with respect to PC resource utilization and cost. Total as well as category-specific utilization and costs including PC, other outpatient care, emergency department use, inpatient care, and pharmaceuticals (chemotherapeutics and other pharmaceuticals evaluated separately) will be assessed to determine how resource use shifts for stepped versus early integrated PC. We will first compare the mean number of outpatient PC visits between the two groups using a linear regression model with adjustment for randomization stratification factors.. Although most utilization and cost outcomes are not normally distributed, based on a sample size of 510, the means would have a normal distribution (central limit theorem). We will also perform the Wilcoxon rank sum test to compare our results to those obtained with the linear regression model.

We will assess the incremental cost-effectiveness of the early integrated PC arm relative to the stepped PC arm from the societal perspective using the average costs and quality adjusted life years (QALYs) accrued under each study arm and as follows: $(\text{Cost}_{\text{early integrated PC}} - \text{Cost}_{\text{stepped PC}}) / (\text{QALY}_{\text{early integrated PC}} - \text{QALY}_{\text{stepped PC}})$.⁶⁵ A \$50,000 per quality-adjusted life-year gained will be considered cost effective.⁶⁶ Costs will include all direct health care costs and indirect (time) costs incurred by patients over their life spans while enrolled in the trial.⁶⁷ The EQ-5D will be used to apply utility weights (quality adjustment) to patients' life spans. Both costs and QALYs will be discounted at a rate of 3%. Based on our prior trials, we expect that few patients will survive past the end of the study period.⁹ Cost and QALY data beyond the end of follow-up for those who are alive will be treated as missing data and estimated using multiple imputation methods. If we find that stepped care is non-inferior to early integrated PC in terms of both QALYs accrued and FACT-L scores, we will ignore QALY data and perform only a cost comparison between the study arms. We will use Monte Carlo methods using 10,000 simulations to incorporate uncertainty in parameter estimates and develop confidence bounds on the estimated cost-effectiveness ratio or the cost difference. Following standard methods of economic evaluation as we have done in other studies, we will also perform parameter-specific sensitivity analyses in which individual parameters are varied singly and in combination, through plausible ranges to assess the relative impact different elements of the program have on overall cost-effectiveness.^{68,69}

